7.1.5.3 Post-Treatment Visits

There will be a protocol driven 30 day follow up visit (see section 7.1.5.3.1) after the last dose of pembrolizumab. Visits to manage toxicity or disease related issues during this period will be scheduled as per the treating physician. The 30 day follow up visit (+/- 5 days) will include prior con med review, adverse event review, exam, vitals, ECOG, CBC and comprehensive serum chemistry, and thyroid function tests.

7.1.5.3.1 Safety Follow-Up Visit

The mandatory Safety Follow-Up Visit should be conducted approximately 30 days after the last dose of trial treatment or before the initiation of a new anti-cancer treatment, whichever comes first. All AEs that occur prior to the Safety Follow-Up Visit should be recorded. Subjects with an AE of Grade > 1 will be followed until the resolution of the AE to Grade 0-1 or until the beginning of a new anti-neoplastic therapy, whichever occurs first.

If it is known, prior to C7D1, that the patient will not achieve the required response, CI, for continuation, the C7D1 and End of Treatment visit will be combined. All study activities for C7D1 will be done except dosing of the study medication. The patient should return 30 days later for the safety follow-up visit.

7.2 Assessing and Recording Adverse Events

An adverse event is defined as any untoward medical occurrence in a patient or clinical investigation subject administered a pharmaceutical product and which does not necessarily have to have a causal relationship with this treatment. An adverse event can therefore be any unfavorable and unintended sign (including an abnormal laboratory finding, for example), symptom, or disease temporally associated with the use of a medicinal product or protocol-specified procedure, whether or not considered related to the medicinal product or protocol-specified procedure. Any worsening (i.e., any clinically significant adverse change in frequency and/or intensity) of a preexisting condition that is temporally associated with the use of the Merck's product, is also an adverse event.

Changes resulting from normal growth and development that do not vary significantly in frequency or severity from expected levels are not to be considered adverse events. Examples of this may include, but are not limited to, teething, typical crying in infants and children and onset of menses or menopause occurring at a physiologically appropriate time.

Merck product includes any pharmaceutical product, biological product, device, diagnostic agent or protocol-specified procedure, whether investigational (including placebo or active comparator medication) or marketed, manufactured by, licensed by, provided by or distributed by Merck for human use.

Adverse events may occur during the course of the use of Merck product in clinical trials or within the follow-up period specified by the protocol, or prescribed in clinical practice, from overdose (whether accidental or intentional), from abuse and from withdrawal.

Adverse events may also occur in screened subjects during any pre-allocation baseline period as a result of a protocol-specified intervention, including washout or discontinuation of usual therapy, diet, placebo treatment or a procedure.

Progression of the cancer under study is not considered an adverse event unless it is considered to be drug related by the investigator.

All adverse events will be recorded from the time the consent form is signed through 30 days following cessation of treatment and at each examination on the Adverse Event case report forms/worksheets. The reporting timeframe for adverse events meeting any serious criteria is described in section 7.2.3.1

7.2.1 Definition of an Overdose for This Protocol and Reporting of Overdose to the Sponsor and to Merck

For purposes of this trial, an overdose of pembrolizumab will be defined as any dose of 1,000 mg or greater (≥ 5 times the indicated dose). No specific information is available on the treatment of overdose of pembrolizumab. Appropriate supportive treatment should be provided if clinically indicated. In the event of overdose, the subject should be observed closely for signs of toxicity. Appropriate supportive treatment should be provided if clinically indicated.

If an adverse event(s) is associated with (“results from”) the overdose of a Merck product, the adverse event(s) is reported as a serious adverse event, even if no other seriousness criteria are met.

If a dose of Merck’s product meeting the protocol definition of overdose is taken without any associated clinical symptoms or abnormal laboratory results, the overdose is reported as a non-serious Event of Clinical Interest (ECI), using the terminology “accidental or intentional overdose without adverse effect.”

All reports of overdose with and without an adverse event must be reported within 24 hours to the Sponsor and within 2 working days hours to Merck Global Safety. (Attn: Worldwide Product Safety; [contact])

7.2.2 Reporting of Pregnancy and Lactation to the Sponsor and to Merck

Although pregnancy and lactation are not considered adverse events, it is the responsibility of investigators or their designees to report any pregnancy or lactation in a subject (spontaneously reported to them), including the pregnancy of a male subject's female partner that occurs during the trial or within 120 days of completing the trial completing the trial, or 30 days following cessation of treatment if the subject initiates new anticancer therapy, whichever is earlier. All subjects and female partners of male subjects who become pregnant must be followed to the completion/termination of the pregnancy. Pregnancy outcomes of spontaneous abortion, missed abortion, benign hydatidiform mole, blighted ovum, fetal death, intrauterine death, miscarriage and stillbirth must be reported as serious events (Important Medical Events). If the pregnancy continues to term, the outcome (health of infant) must also be reported.

Such events must be reported within 24 hours to the Sponsor and within 2 working days to Merck Global Safety. (Attn: Worldwide Product Safety; [contact])

7.2.3 Immediate Reporting of Adverse Events to the Sponsor and to Merck

7.2.3.1 Serious Adverse Events

A serious adverse event is any adverse event occurring at any dose or during any use of Merck's product that:

- Results in death;
- Is life threatening;
- Results in persistent or significant disability/incapacity;
- Results in or prolongs an existing inpatient hospitalization;
- Is a congenital anomaly/birth defect;
- Is a new cancer (that is not a condition of the study);
- Is associated with an overdose;
- Is another important medical event

Refer to Table 10 for additional details regarding each of the above criteria.

Any serious adverse event, or follow up to a serious adverse event, including death due to any cause other than progression of the cancer under study that occurs to any subject from the time the consent is signed through 30 days following cessation of treatment, or the initiation of new anti-cancer therapy, whichever is earlier, whether or not related to Merck product, must be reported within 24 hours to the Sponsor and within 2 working days to Merck Global Safety.

Non-serious Events of Clinical Interest will be forwarded to Merck Global Safety and will be handled in the same manner as SAEs.

Additionally, any serious adverse event, considered by an investigator who is a qualified physician to be related to Merck product that is brought to the attention of the investigator at any time outside of the time period specified in the previous paragraph also must be reported immediately to the Sponsor and the Sponsor will report to Merck.

SAE reports and any other relevant safety information are to be forwarded to the Merck Global Safety [contact]

A copy of all 15 Day Reports and Annual Progress Reports is submitted as required by FDA, European Union (EU), Pharmaceutical and Medical Devices agency (PMDA) or other local regulators. Investigators will cross reference this submission according to local regulations to the Merck Investigational Compound Number (IND, CSA, etc.) at the time of submission. Additionally investigators will submit a copy of these reports to Merck & Co., Inc. (Attn: Worldwide Product Safety; [contact]) at the time of submission to FDA.

All subjects with serious adverse events must be followed up for outcome.

7.2.3.2 Events of Clinical Interest

Selected non-serious and serious adverse events are also known as Events of Clinical Interest (ECI) and must be recorded as such on the Adverse Event case report forms/worksheets and reported within 24 hours to the Sponsor and within 2 working days to Merck Global Safety. (Attn: Worldwide Product Safety; [contact]) Events of clinical interest for this trial include:

1. An overdose of Merck product, as defined in Section 7.1.6 - Definition of an Overdose for This Protocol and Reporting of Overdose to the Sponsor, that is not associated with clinical symptoms or abnormal laboratory results.
2. An elevated AST or ALT lab value that is greater than or equal to 3X the upper limit of normal and an elevated total bilirubin lab value that is greater than or equal to 2X the upper limit of normal and, at the same time, an alkaline phosphatase lab value that is less than 2X the upper limit of normal, as determined by way of protocol-specified laboratory testing or unscheduled laboratory testing.*

*Note: These criteria are based upon available regulatory guidance documents. The purpose of the criteria is to specify a threshold of abnormal hepatic tests that may require an additional evaluation for an underlying etiology. The trial site guidance for assessment and follow up of these criteria can be found in the Investigator Trial File Binder (or equivalent).

7.2.4 Evaluating Adverse Events

An investigator who is a qualified physician will evaluate all adverse events according to the NCI Common Terminology for Adverse Events (CTCAE), version 4.0. Any adverse event which changes CTCAE grade over the course of a given episode will have each change of grade recorded on the adverse event case report forms/worksheets.

All adverse events regardless of CTCAE grade must also be evaluated for seriousness.

Product: MK-3475
Protocol/Amendment No.:

Table 10. Evaluating Adverse Events

An investigator who is a qualified physician, will evaluate all adverse events as to:

V4.0 CTCAE Grading	Grade 1	Mild; asymptomatic or mild symptoms; clinical or diagnostic observations only; intervention not indicated.
	Grade 2	Moderate; minimal, local or noninvasive intervention indicated; limiting age-appropriate instrumental ADL.
	Grade 3	Severe or medically significant but not immediately life-threatening; hospitalization or prolongation of hospitalization indicated; disabling; limiting self-care ADL.
	Grade 4	Life threatening consequences; urgent intervention indicated.
	Grade 5	Death related to AE
Seriousness	A serious adverse event is any adverse event occurring at any dose or during any use of Merck product that:	
	† Results in death ; or	
	† Is life threatening ; or places the subject, in the view of the investigator, at immediate risk of death from the event as it occurred (Note: This does not include an adverse event that, had it occurred in a more severe form, might have caused death.); or	
	† Results in a persistent or significant disability/incapacity (substantial disruption of one’s ability to conduct normal life functions); or	
	† Results in or prolongs an existing inpatient hospitalization (hospitalization is defined as an inpatient admission, regardless of length of stay, even if the hospitalization is a precautionary measure for continued observation. (Note: Hospitalization [including hospitalization for an elective procedure] for a preexisting condition which has not worsened does not constitute a serious adverse event.); or	
	† Is a congenital anomaly/birth defect (in offspring of subject taking the product regardless of time to diagnosis); or	
	Is a new cancer ; (that is not a condition of the study) or	
	Is an overdose (whether accidental or intentional). Any adverse event associated with an overdose is considered a serious adverse event. An overdose that is not associated with an adverse event is considered a non-serious event of clinical interest and must be reported within 24 hours.	
	Other important medical events that may not result in death, not be life threatening, or not require hospitalization may be considered a serious adverse event when, based upon appropriate medical judgment, the event may jeopardize the subject and may require medical or surgical intervention to prevent one of the outcomes listed previously (designated above by a †).	
Duration	Record the start and stop dates of the adverse event. If less than 1 day, indicate the appropriate length of time and units	
Action taken	Did the adverse event cause the Merck product to be discontinued?	
Relationship to test drug	Did the Merck product cause the adverse event? The determination of the likelihood that the Merck product caused the adverse event will be provided by an investigator who is a qualified physician. The investigator’s signed/dated initials on the source document or worksheet that supports the causality noted on the AE form, ensures that a medically qualified assessment of causality was done. This initialed document must be retained for the required regulatory time frame. The criteria below are	

Product: MK-3475

Protocol/Amendment No.:

	intended as reference guidelines to assist the investigator in assessing the likelihood of a relationship between the test drug and the adverse event based upon the available information. The following components are to be used to assess the relationship between the Merck product and the AE; the greater the correlation with the components and their respective elements (in number and/or intensity), the more likely the Merck product caused the adverse event (AE):	
	Exposure	Is there evidence that the subject was actually exposed to the Merck product such as: reliable history, acceptable compliance assessment (pill count, diary, etc.), expected pharmacologic effect, or measurement of drug/metabolite in bodily specimen?
	Time Course	Did the AE follow in a reasonable temporal sequence from administration of the Merck product? Is the time of onset of the AE compatible with a drug-induced effect (applies to trials with investigational medicinal product)?
	Likely Cause	Is the AE not reasonably explained by another etiology such as underlying disease, other drug(s)/vaccine(s), or other host or environmental factors
Relationship to Merck product (continued)	The following components are to be used to assess the relationship between the test drug and the AE: (continued)	
	Dechallenge	Was the Merck product discontinued or dose/exposure/frequency reduced? If yes, did the AE resolve or improve? If yes, this is a positive dechallenge. If no, this is a negative dechallenge. (Note: This criterion is not applicable if: (1) the AE resulted in death or permanent disability; (2) the AE resolved/improved despite continuation of the Merck product; or (3) the trial is a single-dose drug trial); or (4) Merck product(s) is/are only used one time.)
	Rechallenge	Was the subject re-exposed to the Merck product in this study? If yes, did the AE recur or worsen? If yes, this is a positive rechallenge. If no, this is a negative rechallenge. (Note: This criterion is not applicable if: (1) the initial AE resulted in death or permanent disability, or (2) the trial is a single-dose drug trial); or (3) Merck product(s) is/are used only one time). NOTE: IF A RECHALLENGE IS PLANNED FOR AN ADVERSE EVENT WHICH WAS SERIOUS AND WHICH MAY HAVE BEEN CAUSED BY THE MERCK PRODUCT, OR IF REEXPOSURE TO THE MERCK PRODUCT POSES ADDITIONAL POTENTIAL SIGNIFICANT RISK TO THE SUBJECT, THEN THE RECHALLENGE MUST BE APPROVED IN ADVANCE BY THE U.S. CLINICAL MONITOR AS PER DOSE MODIFICATION GUIDELINES IN THE PROTOCOL.
	Consistency with Trial Treatment Profile	Is the clinical/pathological presentation of the AE consistent with previous knowledge regarding the Merck product or drug class pharmacology or toxicology?
The assessment of relationship will be reported on the case report forms /worksheets by an investigator who is a qualified physician according to his/her best clinical judgment, including consideration of the above elements.		

Product: MK-3475
Protocol/Amendment No.:

Record one of the following	Use the following scale of criteria as guidance (not all criteria must be present to be indicative of a Merck product relationship).
Yes, there is a reasonable possibility of Merck product relationship.	There is evidence of exposure to the Merck product. The temporal sequence of the AE onset relative to the administration of the Merck product is reasonable. The AE is more likely explained by the Merck product than by another cause.
No, there is not a reasonable possibility Merck product relationship	Subject did not receive the Merck product OR temporal sequence of the AE onset relative to administration of the Merck product is not reasonable OR there is another obvious cause of the AE. (Also entered for a subject with overdose without an associated AE.)

Product: MK-3475

Protocol/Amendment No.:

7.2.5 Sponsor Responsibility for Reporting Adverse Events

All Adverse Events will be reported to regulatory authorities, IRB/IECs and investigators in accordance with all applicable global laws and regulations.

8.0 STATISTICAL ANALYSIS PLAN

8.1 Statistical Analysis Plan Summary

Data analyses will be performed after the study is completed and the database is released. All statistical programming and analyses will be performed using SAS Version 9.4. Data from participating centers in this protocol will be combined, so that an adequate number of patients will be available for analysis.

For all analyses, data from patients with MPN-AP-BP (exploratory cohort) will be summarized separately, unless otherwise stated.

8.1.1 Analysis Populations

8.1.1.1 Definition of Populations

Full Analysis

The Full Analysis (FA) population includes all patients who received at least one cycle of pembrolizumab and had at least one valid post-baseline efficacy assessment. The FA population will be used for all listings of raw data. Unless otherwise specified, the FA population will be the default analysis set used for all analyses.

Safety

The safety population includes all patients (primary and exploratory cohorts) who received at least one cycle of pembrolizumab and have at least one valid post-baseline safety assessment.

Per Protocol

The Per-Protocol (PP) population will consist of a subset of patients in the FA population who completed 6 treatment cycles and did not have major protocol violations or deviations. This population will be the secondary population for the analysis of the primary efficacy endpoint.

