The choice of the 200 mg Q3W as an appropriate dose for the switch to fixed dosing is based on simulations performed using the population PK model of pembrolizumab showing that the fixed dose of 200 mg every 3 weeks will provide exposures that 1) are optimally consistent with those obtained with the 2 mg/kg dose every 3 weeks, 2) will maintain individual patient exposures in the exposure range established in melanoma as associated with maximal efficacy response and 3) will maintain individual patients exposure in the exposure range established in melanoma that are well tolerated and safe.

A fixed dose regimen will simplify the dosing regimen to be more convenient for physicians and to reduce potential for dosing errors. A fixed dosing scheme will also reduce complexity in the logistical chain at treatment facilities and reduce wastage.

4.2.3 Study Design and Statistical Methods:

This is an open-label phase II trial to assess the efficacy, safety and tolerability of pembrolizumab in patients with PMF, post-PV MF, and post-ET MF. We propose a Simon

Two-Stage design for this study; the first 9 MF patients will be enrolled to confirm a signal of activity and safety of pembrolizumab at the FDA approved dose (in head and neck cancer) of 200mg administered via intravenous infusion over 30 minutes given every 3 weeks for six cycles.

In stage 1, if at least one response (out of 9 subjects in the primary cohort) is observed after six cycles of treatment at week 18, 15 additional patients will be accrued in the second stage (total of 24 evaluable patients in the primary cohort). If however, fewer than 3 of 24 patients respond to therapy, pembrolizumab will be deemed not worthy of any further investigation in this patient population. If response is seen in greater than or equal to 3 of 24 patients, pembrolizumab will be considered to have activity in this patient population and will be recommended for further study. For this study we define inactivity as a response rate of 5%, and activity as a response rate of 25%, which is comparable to that seen with ruxolitinib in a mixed population. The probability of erroneously concluding that the drug has activity if the true but unknown response rate is 5% is 0.10. The power to detect a response rate of 25% with this design is 0.90.

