4.2.4 Rationale for Endpoints

4.2.4.1 Efficacy Endpoint

Primary endpoint:

1. The proportion of treated MF-CP patients (primary cohort) that achieve at least a clinical improvement (CI, PR, CR) by combined European Leukemia Net – International Working Group (ELN-IWG) criteria (Table 5) after 6 cycles of pembrolizumab therapy.

Secondary endpoint:

1. The proportion of treated MPN-AP/BP patients (exploratory cohort) that achieve at least a complete morphologic remission of the leukemic blasts (CR, Cri) by Acute Myeloid Leukemia Response Criteria (Table 6A) within 6 cycles of pembrolizumab therapy.
2. The proportion of treated MPN-AP/BP patients (exploratory cohort) that achieve at least an acute leukemia response-partial (ALR-P, ALR-C, CCR, CMR) using published consensus criteria by Mascarenhas et al. (Table 6B) within 6 cycles of pembrolizumab therapy.

4.2.4.2 Exploratory Endpoints:

1. Assess expression of PD-1/PD-L1 on peripheral blood PB-MNCs, T-cells and CD34+ cells by flow cytometry
2. Assess expression of PD-1/PD-L1 on bone marrow CD34+cells and supporting stromal cells by immunohistochemical staining
3. Assess PD-1/PD-L1 DNA methylation status by bisulfite-sequencing assay
4. Assess status and change in PD-1/PD-L1 expression with response to therapy.
5. Assess changes in driver mutation burden (*JAK2V617F*, *MPLW515L/K*, *CALR*) in granulocytes from treated patients at diagnosis, after 6 cycles and at 1 year of pembrolizumab therapy using the rapid heme panel for next generation sequencing at Brigham and Women's hospital and correlate with response to therapy.
6. Evaluate changes in immune response gene expression profile as well as tumor microenvironment in bone marrow biopsy specimens using nanostring technology after 6 cycles of treatment with pembrolizumab.

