5.9 Subject Replacement Strategy

Patients who do not complete at least one cycle of therapy will be replaced.

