7.1.2 Clinical Procedures/Assessments

Response assessment will formally be conducted after 6 cycles of pembrolizumab therapy, This will include assessment of symptoms, hematologic profile, bone marrow histomorphologic abnormalities, spleen length by manual palpation on physical exam, cytogenetics, and changes in mutational burden from baseline measurement. These established consensus criteria (ELN-IWG) shown in TABLE 5 will allow for uniformity in response assessment and are standardized.

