8.1.1.2 Applicability of Population Efficacy analyses

- The primary efficacy analysis of clinical improvement (CI) or better (partial response (PR) or complete response (CR)) as shown in TABLE 5, will be based on the FA population. A secondary analysis of CI or better (PR or CR) will be performed on the PP population.
- All secondary efficacy analyses will be performed for the FA population.

Product: MK-3475
Protocol/Amendment No.:

Safety analyses

All safety analyses will be based on the safety population. In addition, specific assessments of late toxicity will be performed for patients in the safety population who are followed for safety for at least one year from treatment initiation.

Exploratory analyses

Biomarker analyses will be performed in patients for the FA population.

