8.2.2 Analysis of Efficacy Endpoints

8.2.2.1 8.2.3.1 Primary Endpoint

The primary efficacy endpoint, CI or better (PR,CR) after 6 cycles of treatment as defined by the combined European Leukemia Net –International Working Group (ELN-IWG)) (Table 5) in patients with MF-CP (primary cohort) will be reported as a percentage of the total number of subjects enrolled for both FA and PP populations. A two-sided 90% exact confidence interval for the percentage will be computed using the Clopper and Pearson method.

8.2.2.2 8.2.3.2 Secondary Endpoints

The secondary efficacy endpoint, CRi or better (CR), after 6 cycles of treatment as defined by Acute Myeloid Leukemia Response criteria (Table 6A) in patients with MPN-AP/BP (exploratory cohort) will be reported as a percentage of the total number of subjects enrolled for the FA population.

Product: MK-3475

Protocol/Amendment No.:

The secondary endpoint, ALR-P or better (ALR-C, CCR, CMR), after 6 cycles of treatment as defined using published consensus criteria by Mascarenhas et al. (Table 6B) in patients with MPN-AP/BP (exploratory cohort) will be reported as a percentage of the total number of subjects enrolled for the FA population.

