8.3 Interim Analysis

In addition to periodic safety monitoring, a formal interim analysis will be performed after 9 patients (from the primary cohort) have been assessed at the post cycle six assessments or at the time of withdrawal for those patients not completing six cycles of treatment. If at least one response is observed after six cycles of treatment, 15 additional patients will be accrued in the second stage. If no responses are observed the trial will be terminated.

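### The primary response rate rests on a set defined by post-dose events, cycle-1 failures are replaced whatever the reason, and four denominators are given, so the rate can be biased upward

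*Combined protocol and SAP*

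**What the plan says.** - **Primary set.** Section 8.1.1.2 states that the main analysis of clinical improvement or better, "as shown in TABLE 5, will be based on the FA population". Section 8.1.1.1 says this set "includes all patients who received at least one cycle of pembrolizumab and had at least one valid post-baseline efficacy assessment". It does not say what makes an assessment valid.
- **Replacement.** Section 5.9 reads in full: "Patients who do not complete at least one cycle of therapy will be replaced". No reason for stopping is exempted.
- **Denominator.** Section 4.2.3 plans for a "total of 24 evaluable patients in the primary cohort" and does not define evaluable. Section 4.2.4.1 defines the endpoint as "The proportion of treated MF-CP patients (primary cohort) that achieve at least a clinical improvement". Section 8.2.2.1 says the result "will be reported as a percentage of the total number of subjects enrolled for both FA and PP populations".
- **Interim.** Section 8.3 counts the first 9 primary-cohort patients after cycle 6, "or at the time of withdrawal for those patients not completing six cycles of treatment". This is not repeated for the final analysis, and it does not say how replaced patients are treated.
- **Assessments.** Section 7.1.2 says: "Response assessment will formally be conducted after 6 cycles of pembrolizumab therapy". Blood counts and physical examination (6.1), spleen length (7.1.5.2) and the symptom score (7.1.2.2.1) are nevertheless taken at each visit, and section 7.1.4.1 requires the final-visit activities at discontinuation.
- **Safety set and listings.** The safety set in 8.1.1.1 also requires at least one cycle and a valid assessment. The same section bases raw-data listings on the FA set, whereas 8.2 and 8.2.3.1 call for all data to be listed.

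**The concern.** There is no comparator, so nothing offsets a selective denominator. Response is judged after 6 cycles, and Table 5 requires the benefit to last at least 12 weeks. A patient who stops in cycle 1 is therefore almost certain to be a non-responder. Dropping that patient from the FA set, or filling the place with someone else, can only push the response proportion up.

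Two analysts following the text could report different rates from the same data. Stage 1, where withdrawals count, and the final FA analysis could rest on different populations. The 3-of-24 rule does not say what applies if the FA set is smaller than 24. Replacement could also affect the go/no-go decision, depending on which patients the 5% null rate describes.

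**Working it through.** **Inputs from the plan (4.2.3, 8.2.2.1).** Null rate 5%, target rate 25%. Stop if 0 of 9 respond. Otherwise add 15 patients and declare activity if at least 3 of 24 respond. Stated type I error 0.10 and power 0.90. Two-sided 90% Clopper-Pearson interval. The documents give no early-failure rate, so every loss below is an assumption.

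**1. The plan's own figures.** With X1 ~ Bin(9, p) and X2 ~ Bin(15, p),

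P(active) = P(X1=1)·P(X2≥2) + P(X1=2)·P(X2≥1) + P(X1≥3).

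- p = 0.05: 0.2985 × 0.1710 + 0.0629 × 0.5367 + 0.0084 = 0.0510 + 0.0337 + 0.0084 = **0.093**.
- p = 0.25: 0.2253 × 0.9198 + 0.3003 × 0.9866 + 0.3993 = 0.2072 + 0.2963 + 0.3993 = **0.903**.

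The design is reproduced. An attained error of 0.093 under a nominal 0.10 is normal for a discrete rule. The open question is who fills the 24 places.

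**2. Replacement.** Assume k patients are replaced, all are non-responders, and the true rate is 5% among all 24 + k treated. The rate among the 24 analysed is then 0.05 × (24 + k)/24.

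| k | Rate in the 24 analysed | Type I error |
|---|---|---|
| 0 | 0.0500 | 0.093 |
| 1 | 0.0521 | 0.102 |
| 2 | 0.0542 | 0.111 |
| 3 | 0.0563 | 0.121 |

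The same calculation by share lost, d, uses 0.05/(1 − d). It gives 0.1045 at d = 5%, 0.118 at 10% and 0.152 at 20%. If the 5% instead describes evaluable patients only, the error is 0.093 for any k.

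**3. Exclusion without replacement.** The excluded non-responders add nothing to the count of 3, so the decision rule does not move and the error is at most 0.093. Only the percentage and its interval change. With 3 responders, the minimum for activity:

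| Reading (losses assumed) | Rate | 90% exact interval |
|---|---|---|
| 3/28, all enrolled, 4 replaced | 10.7% | 3.0 to 25.4% |
| 3/24, as planned | 12.5% | 3.5 to 29.2% |
| 3/22, FA set, 2 lost | 13.6% | 3.8 to 31.6% |
| 3/20, FA set, 4 lost | 15.0% | 4.2 to 34.4% |

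**4. How many could be lost.** If per-visit spleen, blood-count and symptom data count as efficacy assessments, the loss is limited to roughly the cycle-1 failures. If only the formal post-cycle-6 assessment counts, it is larger. The text does not settle which.

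**5. Replacement against the sample size.** Section 2.1 caps enrolment at 34, which is 9 + 15 + 10. That leaves no allowance for the replacements required by 5.9 unless the exploratory cohort under-enrols.

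**6. Safety set.** If receiving one cycle means the Day 1 infusion, a patient with a cycle-1 toxicity stays in, because section 5.2.2 requires vital signs after the infusion. If it means a finished 3-week cycle, that toxicity drops out of the summary rates.

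**The case against.** The best case for the plan has five parts.

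- **The null may describe evaluable patients.** Section 4.2.3 sets the 5% and 25% rates in the paragraph that speaks of 24 evaluable patients. On that reading replacement does not inflate the error at all. Otherwise, one replacement exceeds 0.10 by only 0.002. This stands as a condition on the result. It does not settle the matter, because 4.2.4.1 defines the endpoint on treated patients.
- **FA losses are probably few.** Efficacy-type measurements are taken at every visit. If only the post-cycle-6 assessment qualified, the FA set would come close to the Per-Protocol set, so the wider reading is the more natural one. This limits the size of the bias, but it leaves cycle-1 failures out and *valid* undefined.
- **Non-response is partly implied.** A patient in the FA set who stops early has not achieved the endpoint, and 8.3 counts withdrawals at the interim. An explicit rule for the final analysis is still missing, and patients outside the FA set are not covered.
- **Four denominators may be three.** The enrolled wording in 8.2.2.1 can be read as patients within each set. Read literally it would remove the bias, but it would contradict 8.1.1.2.
- **The safety and listing points are minor.** They do not bear on the response rate. Section 8.2.3.1 lists all safety data, so events would not vanish, and the toxicity stopping rule in 11.3 does not use the safety set.

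None of this answers the unconditional replacement rule or the lack of a single stated denominator.

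**Conclusion.** The concern holds and should be fixed. Followed as written, the plan can drop or replace near-certain non-responders, and it does not state one denominator for the primary endpoint. The direction of the bias is upward. Its size cannot be derived from the documents.

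The effect on the decision is conditional: replacement takes the type I error past 0.10 only if the 5% null refers to all treated patients and those replaced are non-responders. Exclusion alone affects only the reported rate and its interval. The Simon calculation is correct, and the toxicity stopping rule is unaffected. The safety-set ambiguity is real but smaller.

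**What to change.** - Define the primary efficacy set as all MF-CP patients who received any pembrolizumab, and count a missing week-18 response as non-response.
- Apply the 1-of-9 and 3-of-24 rules to that set, and use the same denominator in 4.2.3, 4.2.4.1, 8.1.1.1, 8.2.2.1 and 8.3.
- Restrict section 5.9 to patients who were never dosed, and reconcile it with the cap of 34 in section 2.1.
- Keep the Per-Protocol analysis as supportive.
- Define the safety set as any dose received, and base the safety listings on it rather than on the FA set.

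**Cost.** Protocol and SAP wording only, with no extra patients or procedures. The reported rate may be slightly lower. If the 5% and 25% rates apply to all treated patients, the design keeps its error of 0.093 and power of 0.903. If the 25% target holds only among evaluable patients, the rate in the new set is 0.25 × (1 − d). Power is then 0.862 at d = 10% (rate 0.225) and 0.805 at d = 20% (rate 0.20), both shares assumed. Section 4.2.3 should say which population the rates describe and state this cost.
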